7. BACKGROUND AND SIGNIFICANCE

Mood, anxiety, and traumatic stress disorders are prevalent and disabling conditions. These disorders share a number of etiological and clinical similarities, including elevated repetitive negative thinking symptoms (frequent, distressing thoughts about the self and/or the world that are perceived as uncontrollable). Despite slight differences in the clinical presentation of this symptom by disorder (e.g., rumination in depression, worry in anxiety, re-experiencing following trauma), types of repetitive negative thinking load on a single higher order factor rooted in shared neurobiological processes. Addressing repetitive negative thinking in treatment is critical because it relates to the onset, persistence, and recurrence of affective symptoms².

Executive functioning is a hypothesized causal mechanism of transdiagnostic repetitive negative thinking symptoms. Executive functioning is the neuropsychological domain that supports higher-order cognitive activities, including updating and monitoring information in working memory, inhibiting irrelevant information or behaviors, and shifting between mental activities². Neural substrates of executive functioning include the frontoparietal network, consisting of the dorsal anterior cingulate (dACC), dorsal parietal cortex, dorsolateral prefrontal cortex (dlPFC), and the inferior frontal gyrus (IFG). These regions share connections with subcortical and posterior regions in order to maintain goal-directed cognition³¹. Neuropsychological deficits are observed in people with mood, anxiety, and traumatic stress disorders across behavioral (cognitive tests) and neural (functional neuroimaging) indicators of executive functioning³²⁻³⁹. Executive functioning deficits are associated with functional disability and poor quality of life, suicide attempts, and poor treatment response in individuals with these disorders, highlighting the importance of this cognitive domain for well-being and functional outcomes. Repetitive negative thinking is thought to arise from difficulty using executive functioning resources to remove irrelevant information from working memory, causing individuals to get “stuck” in negative thoughts. Thus, executive functioning deficits likely contribute to repetitive negative thinking symptoms in individuals with mood, anxiety, and traumatic stress disorders.

[figure not shown]
Targeted interventions for executive functioning represent an unmet therapeutic need. Estimates of non-response following first-line pharmacotherapy ranges from 30-70% and up to half of patients with mood, anxiety, and traumatic stress disorders do not adequately respond to cognitive behavioral therapy. Executive functioning deficits do not consistently remit in individuals with these disorders who complete standard treatments. Most psychosocial and pharmacological treatments are distal to cognitive mechanisms and only indirectly address cognitive skills. There is a continued need for treatment development to improve clinical response and reduce the burden of these disorders, particularly approaches that address executive functioning.

Targeting executive functioning in treatment would likely result in clinical symptom improvement for several reasons. First, work from our team and others suggest that improving executive functioning directly improves thought regulation, resulting in less repetitive negative thinking. Second, improving executive functioning would likely have helpful downstream effects because repetitive negative thinking exacerbates other clinical symptoms (e.g., negative mood, suicidality), including preceding and predicting worsening affective symptoms. Third, improving executive functioning could mitigate certain stressors that are partially rooted in ineffective cognitive functioning and worsen symptoms. This proposal seeks to test an executive functioning training program previously tested in our group in healthy participants and participants with PTSD in a broader transdiagnostic group of individuals.

8. PROGRESS REPORT

n/a

9. RESEARCH DESIGN AND METHODS

The proposed study is a randomized controlled trial of COGENT versus a no-training control (repeated assessment only) in participants with clinically elevated repetitive negative thinking symptoms. We will use a parallel group design. Primary assessment will include behavioral (cognitive task performance) and imaging-based assessments (fMRI) of control over working memory interference at two time points: baseline pre-training and immediately post-training. Neural activation will be used to assess generalization of training effects across multiple units of analysis. Within the COGENT intervention arm of the study, 8 and 16 sessions will be tested to determine optimal dose. Doses were selected based on our pilot work and empirical recommendations for maximizing cognitive training effects. **Hypotheses:** We hypothesize that COGENT will 1) improve behavioral performance on a cognitive task that assesses control over working memory interference, and 2) increase neural activation within the frontoparietal network during task-based fMRI compared to the control condition. We hypothesize that COGENT will improve symptoms relative to waitlist.

All procedures are considered experimental (i.e., not standard care) and solely for research purposes.

Participants

Approximately **95** participants endorsing elevated mood, anxiety, and/or traumatic stress symptoms who endorse repetitive negative thinking will be recruited and enrolled. Previous validation studies suggest that a cutoff score of 32 on the Repetitive Thinking Questionnaire-10 adequately detects clinically severe repetitive negative thinking. We anticipate that the sociodemographic makeup of the sample will reflect the distribution of biological sex, race, and ethnicity of the San Diego community. As prevalence of internalizing disorders is higher in women than men, it is possible that women may be overrepresented in the sample.

Procedures

Telephone screening: Prior to scheduling a study visit, participants will complete a brief phone screening. This screening will ask specific questions regarding eligibility to reduce participant burden, including questions to assess severity of mood and anxiety symptoms, clear exclusions (e.g., medication and psychotherapy status), and MRI safety. No medical record screening will occur. Participants will complete the Repetitive Negative Thinking Questionnaire-10 (RTQ-10), a psychometrically validated self-report measure that assesses disorder non-specific repetitive negative thinking. Clinically elevated repetitive negative thinking for eligibility purposes is defined as scoring above the cutoff recommended for diverging clinical samples (>32).

Screening Visit and Post Visit 1: Assessment of psychiatric disorders (MINI for DSM-5), past and current suicidality (Columbia Suicide Severity Rating Scale; C-SSRS), medications and treatment history, MRI safety screening, and history of head injury (Ohio State University Traumatic Brain Injury Identification Method Short Form; OSU TBI-ID) will occur during assessment for eligibility. Clinical interview measures will be audio and/or videorecorded for reliability assessment for participants who provide A/V consent.

A comprehensive assessment battery will be used to characterize the sample and measure change from pre to post-training. Participants will complete: a) Demographic Characteristics: PhenX Toolkit Mental Health Research Core Tier 1 assessment. b) Psychopathology symptoms: GAD7 items about anxiety and somatic symptoms. The PhenX Depression measure consists of symptoms from the Quick Inventory of Depressive Symptoms. General psychopathology will be assessed using the PhenX DSM-5 Level 1 Cross-Cutting

Symptom Measure, consisting of 23 questions assessing mental health domains, and the Positive Negative Affect Schedule. PTSD symptoms will be assessed with the PTSD Checklist-5 and the Childhood Trauma Questionnaire will query specific types of PTSD-related events. c) Repetitive negative thinking: Ruminative Response Scale (RRS) includes 22 items about tendencies to dwell on negative thoughts during periods of low mood; and the Penn State Worry Questionnaire (PSWQ) includes 16 items assessing pathological worry; the RNT-10 will be given at the screening visit; the Attention Control Scale will assess difficulty controlling thought content. The emotion regulation questionnaire will assess how participants attempt to control/regulate negative thoughts. D) Physical health and pain: WHODAS will be used to assess current self-rated health, the Insomnia Severity Index will evaluate sleep. e) drug and alcohol screening: the AUDIT, DAST, and PhenX nicotine screeners will be used to evaluate substance use; f) Cognitive assessments: Test My Brain assessments. These tasks ask participants to attend to, memorize, and process stimuli to measure neuropsychological abilities, and include the following tests:

Matrix Reasoning – test of the ability to identify “rules” to a puzzle (viewing a series of visuospatial patterns) and guess the next right answer.

Digit span – assesses working memory and attention. Digits are presented which the participant must repeat back.

Trail making task – measures executive functioning. Participants must draw a line between numbers and letters that are presented in random spatial locations, in the correct serial order.

Digit symbol matching – measures processing speed. Participants are shown a series of digits and must fill in the matching symbol using a “code” provided.

Participants will complete a modified Treatment Credibility Questionnaire for qualitatively assessing acceptability, satisfaction, and feedback about design features. All questionnaires and interviews administered are validated/published measures.

Baseline Visit and Post Visit 2: During the Baseline Visit, further cognitive assessments will be administered. NIH Toolbox Cognition Battery and a computer administered Operation Span task will be administered to further characterize cognitive functioning. This includes the following tests.

Flanker Inhibitory Control and Attention - measures allocation of one's limited capacities to deal with an abundance of environmental stimulation by asking participants to decide on the direction of an arrow that is contained within a row of visual stimuli.

Picture sequence – measures cognitive processes involved in the acquisition, storage and retrieval of new information. Participants are given a word verbally and asked to select the picture that corresponds to the word's meaning.

List sorting – measures the ability to store information until the amount of information to be stored exceeds one's capacity to hold that information. Participants are given a series of words and corresponding images and must recount the items in the correct order.

Oral reading recognition - Measures reading decoding skill and crystallized abilities. The participant is asked to read and pronounce letters and words as accurately as possible.

Dimensional Change Card Sort - The capacity to plan, organize and monitor the executive of behaviors that are strategically directed in a goal-oriented manner. Participants must guess the rule for matching a series of cards and update the rule when the game changes using only correct/incorrect feedback.

Pattern comparison - Assesses the amount of information that can be processed within a certain unit of time. Items are simple so as to purely measure processing speed. Participants are shown a set of two visual stimuli and are asked to choose whether the stimuli are the same or not.

Ospan task - In this task, participants try to memorize stimuli presented on the screen (e.g., letters, numbers) while simultaneously solving math puzzles. Each word appears on the screen, followed by a math puzzle, then another word, and another puzzle, with the number of stimuli ranging from 2 to 7. After a series of items and math puzzles have been presented, a recall screen appears where the participant indicates which items were seen.

Rspan task - In this task, participants try to memorize stimuli presented on the screen (e.g., letters, numbers) while simultaneously deciding if sentences make sense. Each word appears on the screen, followed by a sentence, then another word, and another sentence, with the number of stimuli ranging from 2 to 7. After a series of items and sentences have been presented, a recall screen appears where the participant indicates which items were seen.

Cognitive tasks have been split between the two appointments to minimize cognitive fatigue.

Baseline and Post Visit 2 MRI Assessments: fMRI scanning sessions will occur at baseline and post-training assessment points on a General Electric MR 750 3-Tesla MRI scanner using multiband protocols established by the Human Connectome Project. Each session will consist of a three-plane scout scan (16s), field mapping, a standard anatomic al protocol for standardizing and localizing activation maps) using 3D MPRAGE (TR=2500ms; TE=2ms; TI=1s; flip angle=80; FOV=256x256; 208 sagittal slices; 1mm isotropic voxels [6 minutes 9 seconds]). Functional runs will use a series of BOLD scans collected with Gradient-echo echo planar imaging (EPI) T2* (TR=800ms; TE=30ms; flip angle=520; FOV=216x216mm; 60 axial slices; 2.4mm isotropic voxels). These parameters enable us to cover the entire brain. Functional tasks will include:

Reading Span. This task assesses cognitive control under conditions of high and low interference. In this task, participants try to memorize stimuli presented on the screen (e.g., letters, numbers) while simultaneously solving secondary puzzles (e.g., decide if this sentence makes sense or not). Behavioral outcomes from this task include overall task performance (% correctly recalled stimuli) and reaction times.

Emotional working memory task. In this task, participants view neutral and valenced words, followed by a delay that contains distractor word stimuli. Participants try to remember the words presented to them. Behavioral outcomes from this task include overall task performance (% correctly recalled stimuli) and reaction times.

Participants may also complete resting state (approximately 10 minutes) and additional structural scans (approximately 5 minutes) if time permits, which do not require participant responses. Participant scans will be booked in a one hour block. Participants will complete both scans if they have 15 minutes left following the tasks. They will complete only resting state if they have 10 minutes left following the tasks. They will complete only the structural scan if they have 5 minutes left following the tasks.

COGENT, dose, and randomization: Following the baseline assessments, participants will be randomized to receive COGENT for 4 weeks (n=32) or an assessment-only control condition that receives clinical, cognitive, and MRI assessments at the same time points (n=32), stratified by diagnostic category (primary mood vs. primary anxiety/traumatic stress). In the basic COGENT training program framework, participants will view a series of items to be remembered, following by a secondary processing task where sentence puzzles are

solved. Participants will receive feedback about their accuracy at the conclusion of each set, and an adaptive algorithm will be used to ensure enough difficulty is maintained. The algorithm titrates advancement to the next trial based on meeting at least 85% accuracy on the prior set of trials. Our preliminary data indicate that a session frequency of 8 sessions, delivered twice weekly for 4 weeks (approximately 30 minutes per session) sufficiently improved cognitive performance. Participants assigned to COGENT will be randomized to complete dosing previously established in our work, 8 sessions over 4 weeks or a dosing of 16 sessions over 4 weeks based on literature indicating that training durations of 8 hours may be most effective. Randomization will be generated by [name] and will be securely transmitted to the study coordinator. Task-based adherence data will be collected (number of sessions, frequency). Participants assigned to waitlist will be given the option to complete COGENT after all assessments if they wish.

COVID-19 Considerations: During the COVID-19 crisis, participants may be asked to complete the consenting, screening and screening measures, and cognitive paradigms using HIPAA compliant UCSD Zoom telehealth technology to minimize in-person contact. For in-person tasks, all UCSD and Keck safety procedures will be implemented based on the current Ramp Up phase.

Clinical monitoring: We will administer a brief questionnaire at the treatment mid-point, including the GAD7, PhenX depression, and RNT-10 for purposes of identifying individuals with increased symptoms. Any individual reporting >20% increase in inventories will be referred to the PI for evaluation per the Risk Management plan below.

Table: Assessments by visit	Active groups	Waitlist group
Screening visit MINI CSSRS MRI safety OSU-TBI RNT-10 Demographics GAD-7 Phenx Depression PhenX DSM RRS PSWQ WHODAS CTQ PANAS ACS ERQ PCL-5 AUDIT/DAST/Phenx Nicotine ISI Suicide Cognitions Treatment credibility	X	x
Midpoint clinical check GAD7 Phenx Depression RNT-10	X	
Baseline visit Cognitive assessments MRI	X	X

Cognitive training	X	
Post visit 1 (same as screening visit)	X	X
Post visit 2 (same as baseline visit)	X	X

STATISTICAL DESIGN AND POWER

Primary outcomes: Change in working memory and repetitive negative thinking. To determine whether COGENT engages the target as hypothesized (i.e., improving Ospan behavioral performance), we will analyze the effect of COGENT versus the control on the Ospan total correct score in a 2 (group: combined COGENT conditions, control) x 2 (time: pre-training, post-training) analysis of variance (ANOVA). Our hypothesis will be supported by a significant training by time interaction effect ($p < .05$; medium-large effect size based on power calculations). To investigate optimal dosing of COGENT training, effect size estimates will be compared by dose (8 vs. 16 sessions) for differences in mean change pre- to post-training. This analytic approach will be repeated for the RNT-10 Repetitive Negative Thinking and other symptom measures.

Secondary outcome of cognitive training neural generalization effects: Images will be co-registered using AFNI's 3dvolreg program conducted with the EPI image that results in the smallest adjustment in motion parameters (x, y, z, roll, pitch, yaw). Data will be preprocessed for despiking, censoring outliers, and blurred with an applied Gaussian blur of 4.0mm and transformed into MNI coordinates. The time series of motion parameters will be used to obtain an average for these six motion parameters for each subject, and subjects will be excluded if the average in any one of these parameters exceeds 2 standard deviations from the mean of the distribution of these average motion parameters. A multivariate regressor approach detailed below will be used to relate changes in EPI intensity to differences in task characteristics. A 0-1 reference function will be convolved with a gamma-variate function to model a prototypical hemodynamic response (6-8 second delay) and to account for the temporal dynamics of the hemodynamic response (typically 12-16 seconds). The convolved time series will be normalized and used as a regressor of interest. A series of regressors of interest, polorts for detrending, and the motion regressors will be entered into the AFNI program 3dDeconvolve to determine the height of each regressor for each subject. Voxel-wise normalized relative signal change will be obtained by dividing the regressor coefficient by the sum of the zero-order regressor and the mean first-order regressor. AFNI 3dREML will be used to reduce the false positives induced by cross correlations of the time series.

Group level analyses- the outcomes for the fMRI tasks are the difficulty regressor for the Rspan and emotional working memory tasks. The data will be entered into a mixed effects model, which offers a flexible framework to model the sources of variation and correlation that arise from grouped data (AFNI 3dLME). Once voxel-wise statistics have been calculated, we will use a threshold adjustment based on Monte-Carlo simulations in *a priori* functional regions of interest (ROIs) defined by neuroanatomical atlases of the frontoparietal circuit (NeuroSynth v5 "working memory" Topic 045) with FDR correction ($p < .05$) to guard against identifying false positive activations. The linear mixed effects model will include Group (COGENT vs. control) and Condition (interference vs. baseline) as between-subject factors and Time (pre-training, post-training) as the within-subjects factor, with subject included as a random factor.

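### The RNT-10, a primary outcome, has one visit-based pre-training score, taken before the Baseline Visit; repeating it there would gain precision cheaply

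*Combined protocol and SAP*

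**What the plan says.** All of this is in section 9 of the combined protocol and SAP, except the sample size in section 10.

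- **Outcome and test.** Statistical Design and Power lists working memory and repetitive negative thinking as primary outcomes. Ospan gets a 2 (group) x 2 (time) ANOVA with a dose comparison of mean change, and then: "This analytic approach will be repeated for the RNT-10 Repetitive Negative Thinking and other symptom measures".
- **Eligibility score.** The scale is first completed by telephone, where clinical elevation is defined as "scoring above the cutoff recommended for diverging clinical samples (>32").
- **Pre-training score.** Among the repetitive-thinking measures, "the RNT-10 will be given at the screening visit". That visit's psychiatric, suicidality and MRI-safety assessments "will occur during assessment for eligibility", and the questionnaires serve a second purpose: "A comprehensive assessment battery will be used to characterize the sample and measure change from pre to post-training".
- **Baseline Visit.** The assessment table reads "Baseline visit Cognitive assessments MRI". It is a separate appointment: "Cognitive tasks have been split between the two appointments to minimize cognitive fatigue". Randomisation follows the baseline assessments.
- **Later scores.** The RNT-10 is taken at mid-treatment for clinical monitoring (marked for the active groups only in the table) and at Post Visit 1 in both groups.
- **Sample.** The target is 75 randomised and 65 evaluable; section 9 gives 32 in COGENT and 32 in control.

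No interval or window is given between the screening visit, the Baseline Visit and randomisation.

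**The concern.** The two primary outcomes do not share a starting point. Ospan is measured at the Baseline Visit. The RNT-10 is measured at an earlier visit, while eligibility is still being settled, and not again before training. Each person's RNT-10 change therefore covers the four training weeks plus an undefined stretch before randomisation.

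Two things follow. A change score built on one pre-training measurement carries all of that measurement's occasion-to-occasion variation, which matters with 65 evaluable participants. And if symptoms move between the two visits, each arm's own pre-post change includes that movement, so a within-arm effect size read as the effect of training would be misstated.

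**Working it through.** The plan gives no numerical power calculation, RNT-10 SD, reliability or pre-post correlation, so there is no stated figure to reproduce. The correlations below are assumptions. RTQ-10 and RNT-10 are taken to be the same instrument.

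**Does change before randomisation bias the test?** It is common to the arms in expectation, so it cancels from the group-by-time interaction and from the randomised 8- versus 16-session contrast. A simulation agrees. It used 5,000 trials per setting, 32 per arm, no treatment effect, selection on a phone score above 32, a separate screening-visit score, and an assumed population mean of 34 and SD of 8.

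- Mean drifts of 0, -2 and -4 points after the screening visit gave within-arm changes of about 0, -2 and -4.
- The between-arm difference stayed between -0.05 and +0.04, and type I error between 0.048 and 0.053.
- Selection-driven decline fell between the phone call and the screening visit: about 2.1 points at an occasion-to-occasion correlation of 0.6, and 1.0 at 0.8.

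**What would a second pre-training score buy?** Take unit variances, with *a* the correlation between the two pre-training scores and *r* the correlation of each with the post score.

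- Variance of change, one pre score: 2(1 - r).
- Variance of change, mean of two: (1 + a)/2 + 1 - 2r.
- Proportional cut: (1 - a) / [4(1 - r)].
- Residual variance with baseline adjustment: 1 - r² with one score, 1 - 2r²/(1 + a) with the mean of two.

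Let *a* run from 0.6 to 0.85 and *r* from 0.5 to 0.7, with *a* at least *r* because the two pre-training scores are closer in time. Both cuts shrink as *a* rises and grow as *r* rises, so the extremes are:

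| | a = 0.85, r = 0.5 | a = 0.7, r = 0.7 |
|---|---|---|
| Change variance, one score | 1.000 | 0.600 |
| Change variance, mean of two | 0.925 | 0.450 |
| Cut | 7.5% | 25% |
| Equivalent evaluable | 65/0.925 = 70 | 65/0.75 = 87 |
| Adjusted variance, one score | 0.750 | 0.510 |
| Adjusted variance, mean of two | 0.730 | 0.424 |
| Cut | 2.7% | 17% |
| Equivalent evaluable | 65/0.973 = 67 | 65/0.830 = 78 |

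**In terms of power.** At the favourable end (a = r = 0.7), with 32 per arm and two-sided alpha 0.05, the difference detectable with 80% power is (1.96 + 0.84) x √(2/32) = 0.70 times the SD of the analysed quantity.

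- Change from one score: 0.70 x √0.60 = 0.54 SD; power for a 0.5 SD difference is 0.73.
- Change from the mean of two: 0.70 x √0.45 = 0.47 SD; power is 0.85.
- Baseline adjustment on the single existing score: 0.70 x √0.51 = 0.50 SD; power is 0.80.

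**What averaging does to drift.** Write S, B and P for the screening, baseline and post scores. Then P - (S + B)/2 = (P - B) + (B - S)/2, so half of any screening-to-baseline change stays in the averaged change score.

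**The case against.** The strongest objection is that nothing here is an error. A baseline taken before randomisation is proper practice, the decision rests on a between-arm interaction, and drift before randomisation cancels from it. That stands.

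A reader might infer that selecting people above 32 makes their RNT-10 fall after the screening visit and so inflates every within-arm change. The documents do not support this. The cutoff is described for the phone score, and the screening-visit score is a separate, later administration, so selection-driven decline should fall mainly before it. That would change if the cutoff were reapplied at the visit, which the documents do not say.

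A reader might also infer that drift is present or that the single score is unreliable. Neither can be known: no interval or reliability is given, and the visits may be days apart.

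Two further objections stand in part. The calculation gives both pre-training scores the same correlation with the post score, so it measures the general benefit of a second measurement, not the effect of moving the first one closer to training. And baseline adjustment on the existing score multiplies the change-score variance by (1 + r)/2, a cut of 25% at r = 0.5 and 15% at r = 0.7, without new data. But the plan specifies a group-by-time ANOVA, not that adjustment, and a second score would still add about 3-17% to it.

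**Conclusion.** The point holds as a cheap improvement in precision, not as a correction of bias. The single visit-based pre-training RNT-10, its place before the Baseline Visit and randomisation, and the missing interval are all documented. Arm and dose contrasts remain valid. The gain from a second score is about 7.5-25% of the variance of change, or about 3-17% with baseline adjustment. It depends entirely on the assumed correlations and on *a* being at least *r*.

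Within-arm RNT-10 change is the one quantity that movement before randomisation could distort. The size of any distortion cannot be determined from the documents.

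**What to change.** - Repeat the RNT-10 at the Baseline Visit, before allocation is disclosed, and do not use that score for eligibility.
- Define the pre-training RNT-10 for the primary analysis as the mean of the screening-visit and Baseline Visit scores, and keep Post Visit 1 as the post-training score.
- Report the screening-to-baseline change descriptively.
- Report any within-arm change from the Baseline Visit score alone, because the mean keeps half of any drift.

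The cost is ten questionnaire items at an existing visit, a few minutes per participant, and a short addition to the analysis text. The Baseline Visit and Post Visit 2 batteries, now identical, would differ slightly. No second post-training score is needed.
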